7.3 Discontinuation of Therapy and Withdrawal of the Patients from the Study

Study therapy should be discontinued and the patient should be withdrawn from the study due to any of the following reasons:

- Informed consent withdrawal (the patient has made the decision to stop the participation in study for any reason)
- The patients require other antibiotic treatment
- Development of any adverse event, including serious adverse event, clinical significant deviation in the laboratory results, or concomitant disease, which at the investigator's opinion indicates, that continuation of the study medication administration is not at the patient's best interest
- Pregnancy
- Termination of the study by the Sponsor (e.g. in case of poor safety results)
- Termination of the study by the Regulatory Authority (e.g. in case of poor safety results).

CONFIDENTIAL Page 36 of 88

In all cases the reason of termination of participation in study must be recorded in eCRF. When the patient is withdrawn from the study, all efforts should be made to perform all procedures scheduled for the "early termination visit":

- if the "early termination visit" coincides in time with scheduled visit the procedures of that visit should be done (Section 9.2);
- if the "early termination visit" coincides in time with unscheduled visit the minimum number of procedures should comply with the "End of treatment visit" (Section 9.2.3).

All the patients withdrawn from the study will receive treatment in accordance with the standards adopted in the hospital.

Withdrawn patients will not be replaced.

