9.2.2 Visit 2 (switch to oral therapy/oral therapy, Days 4(8)-7(14) of the study)

Visit 2 is scheduled on Days 4(8)-7(14) of the study and will be performed at hospital.

On Day 4(8) of the study the investigator will assess patient's medical condition and if the patent meets specified criteria he/she (see APPENDIX 2: ASSESSMENT OF CLINICAL STABILITY (POSSIBILITY OF SWITCH TO ORAL TREATMENT)) could be switched to oral treatment. However if the treatment with intravenous IMP should be prolonged after the 7 days of treatment are completed, according to the investigator's opinion, the investigator should contact the study Medical Adviser (see Contact information) for the approval of intravenous treatment prolongation. Despite prolonged intravenous therapy, the overall duration of treatment within this study will not exceed 14 days.

Note that the first dose of oral drug will be administered on the day when the switch is performed (e.g. the patient will receive the first dose of oral drug on Day 4 if the switch is performed at Day 4, etc.). Therefore, oral treatment will be started since Day 4(8) of Visit 2 and will last until and including Day 7(14) of Visit 2.

CONFIDENTIAL Page 49 of 88

Switch to oral therapy (Day 4(8))

All the procedures scheduled on Day 4(8) of Visit 2 should be performed within one day. The following measures will be performed during Day 4(8) of the Visit 2 in accordance with the study schedule of assessments:

- Physical examination (before dosing)
- Assessment of vital signs (before dosing)
- ECG (before dosing; before or 30 minutes after blood samples collection)
- Haematology test (before dosing)
- Biochemical assay (before dosing)
- Urinalysis (before dosing)
- Pulse oximetry (before dosing)
- Collection of a sputum sample for culture (before dosing and if the patient has sputum)
- Collection of a blood sample for culture (before dosing, sampling should not be conducted in case of negative culture at Visit 1)
- Clinical response assessment
- Switch to oral therapy, the first dose of oral IMP
- Assessment of vital signs 2 hours \pm 30 minutes after oral dose administration
- Documentation of AEs/SAEs
- Compliance check
- Assessment of concomitant medication and therapies.

Continuation of oral therapy (Days 5(9)-7(14))

All of the following procedures should be performed on each day of Days 5(9)-7(14) of the study:

- Physical examination before dosing
- Assessment of vital signs before dosing
- Oral therapy with IMP

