10.2.2 Clinical response assessment

The investigator will evaluate clinical response to treatment on Day 4(8) of the study (at Visit 2, switch from intravenous to oral therapy), within 1-2 days (Visit 3, end of treatment) and within 7-9 days (Visit 4, test of cure) after the last dose. Criteria for evaluation of clinical response to the therapy are presented in Table 10-1.

Table 10-1 Criteria for evaluation of clinical response

Category	Criteria
Clinical success	 All signs and symptoms of pneumonia presented at Visit 1 (Day 1) are resolved (i.g., resolution of fever, absence of intoxication, purulent sputum, and respiratory insufficiency) or improved with no worsening or appearance of new signs and symptoms of pneumonia. There is no requirement for additional antibiotic therapy. Chest roentgenograms (CT scans) are cured or improved (only for TOC visit).
Clinical failure	 Persistence or worsening in signs and symptoms of the acute process with either failure to show improvement in the clinical findings, initial improvement in signs and symptoms followed by clinically significant worsening before the assessment. Additional antimicrobial therapy required.

CONFIDENTIAL Page 53 of 88

	 Progression (worsening) of chest roentgenogram (CT scans) abnormalities or unchanged chest roentgenogram features (only for TOC visit).
	 Death because of pneumonia.
Indeterminate	• No evaluation possible: the patient was lost to follow-up, or died
	because of noninfectious-related reasons or infection other than
	pneumonia (as judged by the investigator).

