12.6.2 Primary efficacy analysis

The percentage and the number of patients with different categories of clinical response ("clinical success", "clinical failure", "indeterminate") will be summarized by treatment group in mITT and CE populations for Visit 2 (switch to oral therapy), Visit 3 and Visit 4.

The percentage of patients with clinical success (as judged by the investigator) at the test of cure Visit 4 is defined as primary endpoint variable.

In regards to efficacy for CAP, non-inferiority of Nemonoxacin compared to Tavanic[®] will be evaluated for clinical response by using a one-sided 95% confidence interval for the difference in the primary efficacy endpoint (investigational drug minus comparator). Non-inferiority of Nemonoxacin will be stated if the lower boundary of the estimated one-sided 95% confidence interval for the difference in the clinical success rate of Nemonoxacin and Tavanic[®] is above -15% the Farrington-Manning test.

CONFIDENTIAL Page 65 of 88

The primary analysis will be performed in the mITT population.

If non-inferiority is shown, a test on superiority will be performed in addition using the two-sided 95% confidence interval. The test on superiority is significant, if the lower two-sided 95% confidence interval limit is above "0".

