12.6.3 Secondary efficacy analyses

As a supportive analysis, the primary efficacy endpoint will be analyzed in the CE population using the same method as that used for the primary efficacy analysis.

For secondary efficacy analyses, the clinical success rates of the patients in the mITT and CE populations at Visit 2 (switch to oral therapy) and Visit 3 as well as the number (proportion) of patients who needed other antibiotic treatment (treatment failure) will be analyzed using a two-sided 95% confidence interval (equality test) calculated based on the same statistical test as for the primary analysis.

Additionally, the results of statistical comparison of the clinical success rates using the logistic regression will also be provided.

Time to switch therapy from i.v. to oral therapy will be evaluated using the Kaplan – Meier survival analysis method and compared by log-rank test between treatment groups. The Kaplan-Meier curves will be presented graphically.

Microbiological efficacy endpoints will include microbiological success rates evaluated per each patient and by identified pathogens in b-mITT and BE.

The percentage and the number of patients with microbiological success and failure will be summarized by visit and treatment group. Microbiological success is defined as the assessments of eradication and presumed eradication. Other results of assessments (excluding unevaluable) will be regarded as microbiological failure. The difference between microbiological success rates and its CI will be calculated using the same method as that used for the secondary efficacy endpoints.

The percentage and number of the baseline-identified strains (sputum and blood culture) with microbiological success and failure will be summarized by visit and treatment group. The frequency of each category and sample source (sputum and blood culture) will be presented separately and by treatment group. Microbiological data by identified pathogens will be analyzed descriptively.

Microbiological efficacy evaluation

Based on the results of culture (bacteriological) study the microbiological response will be assessed. Microbiological response is defined as:

- 1. Eradication (admission pathogen[s] is absent),
- 2. Presumed eradication (if no material available for culture because of clinical success)
- 3. Persistence (admission pathogen[s] is present),
- 4. Presumed persistence (no material available for culture for patients with clinical failure),

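### Withdrawal for another antibiotic, or death, before the i.v.-to-oral switch is a competing event in time to switch; with ordinary censoring, an early excess of i.v. failures drops out of that endpoint

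*Combined protocol and SAP*

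**What the plan says.** Section 12.6.3 gives time to switch two sentences. One sets the method: "Time to switch therapy from i.v. to oral therapy will be evaluated using the Kaplan", that is, Kaplan-Meier curves with a log-rank test of the two arms. The other asks for a plot. No section names the analysis population, the censoring rule or the handling of patients who never switch. Section 12.4 sets a two-sided 5% level for analyses other than the primary one.

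Section 7.3 stops study therapy and withdraws the patient for several reasons, among them "The patients require other antibiotic treatment". It adds: "In all cases the reason of termination of participation in study must be recorded in eCRF". Section 6.1 requires at least 3 days of i.v. treatment, so Day 4 is the first possible switch day. I.v. treatment may run to Day 7, or longer after contact with the Medical Adviser, but under section 9.2.2 "the overall duration of treatment within this study will not exceed 14 days".

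Other endpoints also bear on i.v. failure. Section 12.6.3 compares "the clinical success rates of the patients in the mITT and CE populations at Visit 2 (switch to oral therapy) and Visit 3", and the proportion needing another antibiotic. Table 10-1 lists "Additional antimicrobial therapy required" and death from pneumonia under clinical failure. Section 12.1 admits to mITT only patients evaluated for efficacy at least once. Section 12.5 leaves missing data to a statistical analysis plan, which section 12.9 says will be final before database close-out.

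**The concern.** A patient withdrawn during the i.v. phase for another antibiotic, or who dies, will never switch to the oral study drug. That is not incomplete follow-up; it is a different outcome that rules out the event. Kaplan-Meier with ordinary censoring treats such a patient as someone who would have gone on to switch like the rest. The curve then estimates switching in a setting without i.v. failure, and the log-rank compares the rate of switching among patients still on i.v. therapy.

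Comparing the two i.v. forms is a secondary objective (section 4.2), and time to switch is one of the few endpoints confined to the i.v. phase. A drug with more i.v. failures could show the same switch curve as its comparator.

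Visit 2 clinical response has a smaller gap of the same kind: no sentence says how a withdrawal before the Visit 2 assessment is scored at Visit 2.

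**Working it through.** The plan gives no event count, effect size or power for time to switch, so there is no figure of its own to reproduce.

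**Inputs from the documents.** 171 randomized per arm, giving about 137 in mITT (section 12.10; 171 × 0.80 = 136.8); two-sided 5% (12.4); no switch before Day 4 (6.1); Day 14 as the horizon (9.2.2); up to two-thirds meeting switch criteria in the first 3 days (3.5).

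**Assumptions.** I.v. failure 15% on test and 5% on comparator, spread evenly over a stated window. Every other patient switches on Days 4–8 with the same pattern in both arms. Four patterns were used (share on Days 4/5/6/7/8):
- A: 67/13/10/5/5%
- B: 50/20/15/10/5%
- C: 50/20/12/10/8%
- D: 67/15/8/6/4%

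**Step 1: the curve.** Take pattern A with failures on Days 2–3.
- Remaining at risk on Day 4: 137 × 0.85 = 116.5 and 137 × 0.95 = 130.2.
- Expected Day 4 switches: 0.67 × 116.5 = 78.0 and 0.67 × 130.2 = 87.2.
- Kaplan-Meier, failures censored: 78.0/116.5 = 67% and 87.2/130.2 = 67%.
- True proportion switched: 78.0/137 = 57% and 87.2/137 = 64%.

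By Day 8 the censored curve reaches 100% in both arms, against true values of 85% and 95%. With failures on Days 5–8 (pattern C) it reaches 93% and 98%. With all failures on Day 8 it gives the true 85% and 95%.

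**Step 2: the test.** Simulated log-rank rejection at 15% vs 5%, 137 per arm (4000–6000 runs per setting for A and B, 1500 for C and D). Kept means at risk as not switched to Day 14.

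| Failure window | Patterns | Censored | Kept |
|---|---|---|---|
| Days 2–3 | A, B, C, D | 5.4, 5.1, 5.6, 5.4% | 68.9, 64.4, 63.5, 69.3% |
| Days 2–5 | A, B | 9.5, 8.0% | 68.9, 64.0% |
| Days 3–6 | A, B | 19.1, 14.1% | 68.7, 64.6% |
| Days 2–7 | C, D | 16.5, 21.5% | 64.3, 66.7% |
| Days 4–7 | A, B | 36.8, 29.4% | 68.9, 64.1% |
| Days 5–8 | C, D | 42.3, 55.3% | 62.1, 68.3% |
| Day 8 only | C, D | 62.5, 69.7% | 62.5, 69.7% |

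A further run for Days 5–8 under pattern A gave 56% and 69%.

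At 10% vs 5% the kept analysis has only 21–27% power. At 20% vs 5% it has 91–94%, and the censored log-rank ranges from 4–5% (Days 2–3) to 74% (Days 5–8). With 171 per arm, 15% vs 5% and failures on Days 2–3, the pair is 4.4% vs 73.9%. With equal failure rates both analyses reject in about 5% of runs.

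**Step 3: the other direction.** With 5% failures in both arms and a slower test drug (52% vs 67% switching on Day 4), the censored log-rank has 38–46% power and the kept analysis 26–28%.

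**Step 4: what else can show the excess.** A score test on need for another antibiotic at 15% vs 5% has 81% power, or 65% at 20% vs 10% if 5 points of later failures are added to each arm. Visit 2 success over all mITT, with earlier failures as non-success, has 62% power if 95% of the rest succeed (48–73% for 90–98%).

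**Step 5: Visit 2.** An unscheduled early termination visit carries at least the End of treatment procedures (sections 7.3 and 9.3), which include clinical response (9.2.3), so a failure can be recorded there. But no text says that it counts at Visit 2. If the withdrawal coincides with Visit 1, the procedures of that visit apply, and Table 9-1 has no clinical response assessment at Visit 1. Such a patient, or one who dies unassessed, may miss the mITT entry rule. CE does not help: fewer than 7 days of study drug is a protocol violation (12.2), which excludes the patient from CE.

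**The case against.** The strongest reply is that censoring rules are SAP-level detail, and sections 12.5 and 12.9 promise a separate plan. This stands as a condition: if that plan already sets the rule, the point falls away. Section 12.5 speaks of missing data, however, and a competing event is not missing data.

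Second, the log-rank with failures censored is a valid test of its own question. It holds its 5% level and is the more sensitive of the two to pure slowness. This also stands, and is why the planned test should be kept and labelled rather than dropped.

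Third, failures are compared elsewhere, and need for another antibiotic has 81% power in the illustration, more than the repaired time to switch. That is so, but that endpoint covers the whole course rather than the i.v. phase alone.

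Some stronger readings are tempting, and the documents do not support them:
- A reader might infer that the plan prescribes censoring of failures. It says nothing either way.
- A reader might infer that any excess of i.v. failures would be missed. Late failures lose little, and failures on or after the last switch day lose nothing. I.v. treatment to Day 7 or beyond makes late failures possible.
- A reader might infer that both curves would reach 100%. That follows from assuming that every non-failing patient switches by Day 8, whereas the plan allows longer i.v. treatment.
- A reader might infer that a failing drug would look faster. In a constructed extreme, where the slowest 15% switch on Day 8 on comparator but fail on Day 3 on test, this happens in 94% of runs. Nothing in the documents suggests that pattern.

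**Conclusion.** The point holds as a gap in one secondary endpoint, worth closing because it is cheap. Withdrawal for another antibiotic and death before the switch are competing events, and the plan names a method without saying how they enter it. Under ordinary censoring the curve overstates the proportion switched unless the failures fall on or after the last switch day. An excess of i.v. failures is lost wholly if it falls before Day 4, partly if between switch days, and not at all if on or after the last switch day.

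The sizes rest on assumed failure rates, failure timing and switch patterns, and on equal switch speed among the other patients; the documents supply none of these apart from the two-thirds figure. The direction held across all settings in the table except Day 8, where the two analyses agree. Nothing here touches the primary endpoint, and the trial is not blind to i.v. failures.

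**What to change.** In section 12.6.3 or the statistical analysis plan:

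1. Name the population for time to switch: all randomized patients who received study drug, so that those who die or leave unassessed are not lost through the mITT entry rule.
2. Estimate the cumulative incidence of switch, with withdrawal for failure or another antibiotic, and death, as competing events, and compare arms by Gray's test. Keeping these patients at risk as not switched to Day 14 is equivalent only if there is no other censoring.
3. Count patients who complete treatment on i.v. as not switched, and state how withdrawals for adverse events or consent are handled.
4. Report the planned log-rank with failures censored beside it, labelled as speed of switch among patients still on i.v. therapy. This covers the competing-event analysis's weaker sensitivity to pure slowness.
5. For Visit 2, state that a clinical failure recorded at an early termination visit before the Visit 2 assessment, or an earlier withdrawal for another antibiotic or death from pneumonia, counts as non-success, and that such patients count as evaluated for mITT.

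The cost is a few sentences before database close-out. Withdrawal reasons (7.3) and changes in concomitant therapy (8.7) already go into the eCRF, so no visit, procedure, data item or change in sample size is needed. Item 5 may add a few patients to mITT, which is also the primary analysis population, so it should be settled before the blind is broken.

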oral therapy at Day 4(8) of the study if the specific criteria of clinical stability are achieved. The treatment will be continued with appropriate oral therapy. If the patient receives i.v. therapy with Nemonoxacin he/she will continue oral therapy with Nemonoxacin 250 mg, 2 capsules per day. If the patient receives i.v. therapy with Tavanic[®] he/she will continue oral therapy with Tavanic[®] 250 mg, 2 over-encapsulated film coated tablets per day.

The duration of oral therapy will be judged by investigator and oral therapy will last until and including Day 7(14) of the study.

The study includes 5 visits:

- 1. Visit 1 (Screening /randomization/ intravenous therapy, Days 1-3(7) of the study)
- 2. Visit 2 (Switch to oral therapy /oral therapy, Days 4(8)-7(14) of the study)
- 3. Visit 3 (End of treatment visit, within 1-2 days after the last dose)
- 4. Visit 4 (Test of cure visit, within 7-9 days after the last dose)
- 5. Visit 5 (Long-term follow-up visit; within 21-23 days after the last dose).

Number of Subjects:

A total of 342 eligible patients (171 patients per test group) will be enrolled and randomized in the study. Presumably screening of 382 patients will allow randomization of 342 patients.

Inclusion Criteria:

- 1. Written informed consent obtained from the patient.
- 2. Female and male patients aged between 18 and 70 years inclusive.
- 3. Patients with moderate to severe community-acquired pneumonia who need inpatient treatment (correspodence to at least one of the criteria for hospitalization / preferred hospitalization described in the Appendix 1 of this protocol) but do not need ICU treatment (in case of correspondence to at least one «major» or three «minor» criteria for hospitalization in intensive care unit described in Appendix 1 of this protocol, patient should not be enrolled in the study).
- 4. The presence of at least 3 of the following symptoms/signs:
 - Cough
 - Purulent sputum production
 - Tachypnea (respiratory rate > 24 breaths/minute)
 - Chills
 - Fever (rectal/ tympanic temperature ≥ 38.5°C or axillary/ oral/ cutaneous temperature ≥ 38.0°C)
 - WBC count of $\geq 10.0 \text{ x } 10^9/\text{L}$ or $\geq 15\%$ immature

CONFIDENTIAL Page 17 of 88

neutrophils (bands; regardless of peripheral WBC count).

- 5. Radiological evidence of (a) new infiltrate(s) consistent with bacterial pneumonia at baseline.

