7 SELECTION OF STUDY POPULATION

7.1 Inclusion Criteria

Patients will be eligible for inclusion in the study only if all of the following inclusion criteria are applied:

- 1. Written informed consent obtained from the patient.
- 2. Female and male patients aged between 18 and 70 years inclusive.
- 3. Patients with moderate to severe community-acquired pneumonia who need inpatient treatment (correspondence to at least one of the criteria for hospitalization / preferred hospitalization described in the Appendix 1 of this protocol) but do not need ICU treatment (in case of correspondence to at least one «major» or three «minor» criteria for hospitalization in intensive care unit described in Appendix 1 of this protocol, patient should not be enrolled in the study).
- 4. The presence of at least 3 of the following symptoms/signs:
 - Cough
 - Purulent sputum production
 - Tachypnea (respiratory rate > 24 breaths/minute)
 - Chills
 - Fever (rectal/ tympanic temperature $\geq 38.5^{\circ}\text{C}$ or axillary/ oral/ cutaneous temperature $\geq 38.0^{\circ}\text{C}$)
 - WBC count of $\ge 10.0 \text{ x } 10^9/\text{L}$ or $\ge 15\%$ immature neutrophils (bands; regardless of peripheral WBC count).
- 5. Radiological evidence of (a) new infiltrate(s) consistent with bacterial pneumonia at baseline.
- 6. Treatment-naive patients or patients who have received single dose of a short-acting antibacterial drug within 24 hours of enrollment or patients with treatment failure who have received antibiotics (with the exception of quinolones or fluoroquinolones) for less than 72 hours.
- 7. Consent to use contraception during participation in the study (for women childbearing potential and men).

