APPENDIX 2: ASSESSMENT OF CLINICAL STABILITY (POSSIBILITY OF SWITCH TO ORAL TREATMENT)*

- 1. Cough and shortness of breath improving.
- 2. Patient afebrile for ≥24 hours (axillary temperature <37.2°C, or equivalent for oral, tympanic, or rectal temperature), on 2 or more measurements at least 24 hours apart, with no known spiking of temperature during that interval.
- 3. Possibility of oral intake and gastrointestinal tract absorption adequate.

CONFIDENTIAL Page 76 of 88

APPENDIX 3: DRUGS THAT MAY PROLONG THE QT INTERVAL WITH KNOWN RISK OR POSSIBLE RISK OF TORSADES DE POINTES (TDP)

Generic Name	Drug Class	Therapeutic Use	TdP Risk Category
Azithromycin	Antibiotic	Bacterial	Drugs with possible TdP risk
		infection	
Alfuzosin	Alpha1-blocker	Benign prostatic	Drugs with possible TdP risk
		hyperplasia	
Amiodarone	Anti-arrhythmic	Abnormal heart	Drugs with known TdP risk
		rhythm	
Anagrelide	Phosphodiesterase	Thrombocythemi	Drugs with known TdP risk
	3 inhibitor	a	
Apomorphine	Dopamine agonist	Parkinson's	Drugs with possible TdP risk
		disease	
Aripiprazole	Anti-psychotic,	Psychosis,	Drugs with possible TdP risk
	atypical	Adjunct for	
		Depression	
Astemizole	Antihistamine	Allergic rhinitis	Drugs with known TdP risk
Atazanavir	Anti-viral	HIV/AIDS	Drugs with possible TdP risk
Bedaquiline	Antibiotic	Tuberculosis,	Drugs with possible TdP risk
		drug resistant	
Bepridil	Anti-anginal	Angina Pectoris	Drugs with known TdP risk
		(heart pain)	
Bortezomib	Proteasome	Multiple	Drugs with possible TdP risk
	inhibitor	Myeloma,	
		lymphoma	
Bosutinib	Tyrosine kinase	Leukemia	Drugs with possible TdP risk
	inhibitor		
Vandetanib	Anti-cancer	Thyroid cancer	Drugs with known TdP risk
Vardenafil	Phosphodiesterase	Vasodilator	Drugs with possible TdP risk
	inhibitor		
Vemurafenib	Kinase inhibitor	Anti-cancer	Drugs with possible TdP risk
Venlafaxine	Anti-depressant,	Depression	Drugs with possible TdP risk
	SNRI		
Vorinostat	Anti-cancer	Lymphoma	Drugs with possible TdP risk
Halofantrine	Anti-malarial	Malaria infection	Drugs with known TdP risk

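### The unstratified log-rank test for time to oral switch ignores baseline temperature, which probably drives when a patient can switch; stratifying on it could recover some sensitivity at almost no cost

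*Combined protocol and SAP*

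**What the plan says.** **Entry.** Inclusion criterion 4 (Section 7.1) asks for "The presence of at least 3 of the following symptoms/signs". Fever is one of six items, with a threshold of "axillary/ oral/ cutaneous temperature ≥ 38.0°C" (0.5°C higher for rectal or tympanic readings). Cough, purulent sputum and a raised white cell count are enough without it. Inclusion criterion 3 does not require fever either, because temperature is only one of many hospitalization criteria in Appendix 1.

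**Switch.** Appendix 2 lists three criteria:
- "Cough and shortness of breath improving", with no minimum change and no confirmation;
- "Patient afebrile for ≥24 hours (axillary temperature <37.2°C, or equivalent for oral, tympanic, or rectal temperature"), established "on 2 or more measurements at least 24 hours apart, with no known spiking of temperature during that interval";
- "Possibility of oral intake and gastrointestinal tract absorption adequate".

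Intravenous treatment lasts at least 3 days and the investigator may extend it to 7 (Section 6.1), so the first possible switch is Day 4.

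**Analysis.** Section 12.6.3: "Time to switch therapy from i.v. to oral therapy will be evaluated using the Kaplan"-Meier method, with a log-rank comparison of the arms. No stratification or baseline covariate is named for this endpoint. Section 8.5 names no randomization strata. Section 12.4 sets the two-sided 5% level. Section 10.3.2 has temperature measured before the first dose.

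**The concern.** Of the three switch criteria, only temperature is tied to a measured value, and some patients may already be on the right side of it when they are randomized. For them the temperature criterion can be settled before Day 4, and what remains is a judgement about cough, dyspnoea and oral intake. For a patient who enters febrile, the temperature has to come down and stay down first. The two kinds of patient are likely to have quite different switch times in either arm.

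A log-rank test that pools them treats this predictable difference as noise. It remains valid, but it may be less sensitive than it could be. Time to switch is one of the few endpoints that bear on the secondary objective of comparing the intravenous drugs (Section 4.2). The trial is built around non-inferiority, so a non-significant result from an insensitive test could be read as support for similarity.

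**Working it through.** **1. When the temperature criterion can be met.** It needs two readings at least 24 h apart. From study readings, a patient below 37.2°C on Day 1 can satisfy it on Day 2 at the earliest. That is before the Day 4 floor, so for such a patient temperature need not delay the switch.

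**2. Who these patients are.** The entry fever item starts at 38.0°C axillary and the switch limit is 37.2°C. A patient at 37.2 to 37.9°C lacks the entry sign of fever but does not meet the switch criterion. The relevant factor is therefore the Appendix 2 limit, not the absence of entry fever.

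**3. Inputs.** The plan gives no power or sample-size figure for time to switch, so there is nothing to reproduce.
- From the documents: 137 per arm (Section 12.10, used for illustration); up to two-thirds of patients ready to switch within 3 days (Section 3.5); switch days 4 to 8; two-sided 5%.
- Assumed: share *f* below the limit at baseline, 10% to 40%; switch-rate ratio 0.65 or 0.70; behaviour of the patients below the limit.

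**4. Why stratifying helps, by hand.** Take *f* = 0.30, two-thirds switching on Day 4 overall, and 90% of the below-limit group doing so. The others then switch on Day 4 at (0.667 − 0.30 × 0.90)/0.70 = 0.567. Per-patient variance of Day 4 switching, with no arm difference:
- pooled: 0.667 × 0.333 = 0.222;
- within strata: 0.30 × 0.90 × 0.10 + 0.70 × 0.567 × 0.433 = 0.027 + 0.172 = 0.199.

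That is about 10% less variance for the same comparison. If both groups share a rate ratio, pooling also attenuates the apparent effect, and stratifying recovers this too.

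**5. Simulated log-rank power.** Times to stability are exponential, events are placed on Days 4 to 8, and later ones are censored. In A to C, two-thirds switch on Day 4 overall and the ratio in the other patients is 0.65.

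| Assumption for patients below the limit | Test | *f* = 10% | 20% | 30% | 40% |
|---|---|---|---|---|---|
| A: 90% switch on Day 4, no drug effect | planned | 83.8% | 76.1% | 66.4% | 54.5% |
| | stratified | 84.4% | 77.0% | 68.0% | 56.5% |
| | restricted to the others | 85.6% | 80.4% | 73.0% | 63.4% |
| B: 90% switch on Day 4, same ratio 0.65 | planned | 87% | 84% | 79% | 71% |
| | restricted to the others | 85% | 81% | 75% | 64% |
| C: two-thirds switch on Day 4, same ratio 0.65 | planned | 90% | 89% | 90% | 89% |
| | restricted to the others | 86% | 83% | 78% | 70% |

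Stratifying gains 0.6 to 2.0 points in A. In B it gains from about 1 point at 10% to about 12 at 40%. In C it changes power by no more than 0.5 point.

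A harsher variant has every below-limit patient switching on Day 4 in both arms and a ratio of 0.70 in the rest. At *f* = 10% and 40%, stratifying moves power:
- from 71.3% to 72.7% and from 49.2% to 54.2%, if two-thirds of the remaining comparator patients are stable by day 3;
- from 55.7% to 59.2% and from 33.6% to 43.6%, if 40% are.

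If only half of the below-limit patients are certain Day 4 switchers, at *f* = 30%, the gains are 0.3 point (68.3% to 68.6%) and 1.6 points (51.6% to 53.2%).

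**6. Type I error.** With no difference between arms, the planned, stratified and restricted tests reject in 4.4% to 5.7% of simulated trials.

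**The case against.** The strongest objection is to a wider claim that a reader might infer: that patients without fever at entry meet the switch criterion on Day 1, switch on Day 4 whatever the drug, and so dilute the comparison to the point where the main reading should exclude them. The documents do not support this. Two readings 24 h apart are needed. Lacking entry fever is not the same as being below 37.2°C. Cough and dyspnoea must still improve, and the investigator may prolong treatment, so a drug effect can remain in these patients. If it does, restricting the analysis loses power: up to 7 points in B (71% to 64%) and up to 19 in C (89% to 70%). Restriction also changes the population to which the result applies.

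Other objections stand in part:
- **Day 4 ties.** Much of the clustering comes from the 3-day minimum. With up to two-thirds of patients ready by then, febrile entrants tie on Day 4 too. This limits what stratifying can recover.
- **Antipyretics.** They are allowed on the first two treatment days and barred from Day 3 (Sections 8.7.1 and 8.7.2). Early readings may be masked, and a later spike would undo the criterion. This weakens the link between baseline temperature and switch day but does not remove it.
- **Consequence.** This is one secondary endpoint with no power claim. Clinical success and microbiological response at Visit 2 also bear on the intravenous objective.
- **Separate plan.** Section 12.9 leaves detail to a statistical analysis plan to be finalized before database close-out. A stratified test may be specified there.

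None of this argues against stratifying, which keeps all patients and showed no material loss in any setting tried.

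**Conclusion.** The point holds as a modest loss of efficiency. Fever is optional at entry, temperature is the only numeric and confirmed switch criterion, and the stated test ignores a baseline value that probably predicts switch day. That it is a strong predictor is an inference from the criteria; the documents report no data on it.

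The gain from stratifying is roughly 0 to 12 points of power. It is near zero if patients below the limit switch no earlier than others, and largest if they switch early, share the drug effect and make up 40% of the trial. The range rests on an assumed 10% to 40% below the limit and assumed ratios of 0.65 to 0.70, none of which is in the documents. The planned test is valid as it stands. The change is worth making because it costs almost nothing, not because the present plan would mislead.

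**What to change.** In Section 12.6.3, or in the statistical analysis plan before it is finalized:

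1. Stratify the log-rank test for time to switch by whether the Visit 1 pre-treatment temperature was below the Appendix 2 limit (37.2°C axillary or equivalent).
2. Show the Kaplan-Meier curves by arm within each stratum.
3. State how readings taken by other routes are classified for this factor, since Appendix 2 refers to equivalents without listing them.
4. If an analysis of patients not below the limit is wanted, label it a descriptive sensitivity analysis and do not make it the main reading.

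The cost is a few lines of text and one extra display. Temperature is already collected before treatment. Entry rules, switch rules, treatment and sample size stay as they are.
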